### 1.3 RATIONALE FOR PERFORMING THE TRIAL

As a transition from non-clinical investigations to clinical development, in this first-in-man trial, safety, tolerability, pharmacokinetics and pharmacodynamics of BI 764112 will be assessed in healthy male volunteers, using single rising oral doses in order to provide the basis for the clinical development of BI 764112, a first-in-class, selective vanin inhibitor, in the indication of CD.

Young, healthy male subjects will be recruited for this study. They (1) provide a relatively stable physiological, biochemical and hormonal basis for studying drug effects, (2) show no disease-related variation and (3) are not taking regular concomitant medications.

In the single rising dose (SRD) parts, within each DG, all actively treated individuals will receive the same BI 764122 dose. The next higher dose will only be administered to the next group, if the treatment in the preceding DG was safe and showed acceptable tolerability.

In the food effect (FE) part, BI 764112 will be administered to subjects in a randomized two-way-crossover fashion to (1) understand the effect of food on relative bioavailability, (2) support upcoming clinical studies with respect to improved trial designs and (3) optimize trial formulations.

### 1.3.1 Starting dose

#### Maximum recommended starting dose (MRSD)

An estimation was made on the basis of the US FDA Guidance for Industry 'Estimating the Maximum Recommended Safe Starting Dose in Initial Clinical Trials for Therapeutics in Healthy Volunteers' [[R06-1037](#)].

#### *Step 1: Determination of NOAELs in the safety pharmacology and toxicity studies*

Rat: 300 mg/kg/day NOAEL for general toxicology in the 4-week rat toxicity study

Dog: 100 mg/kg/day NOAEL for general toxicology in the 4-week dog toxicity study

#### *Step 2: Conversion of animal NOAELs to Human Equivalent Doses (HEDs)*

Rat: NOAEL = 300 mg/kg/day

Conversion factor from rat dose to HED: 6.2

$$\text{HED} = 300 \text{ mg/kg/day} \div 6.2$$

$$= 48 \text{ mg/kg/day}$$

i.e. 2880 mg/day in humans (assuming a body weight of 60 kg)

Dog: NOAEL = 100 mg/kg/day

Conversion factor from dog dose to HED: 1.8

$$\text{HED} = \text{mg/kg/day} \div 1.8$$

$$= 56 \text{ mg/kg/day}$$

i.e. 3360 mg/day in humans (assuming a body weight of 60 kg)

#### *Step 3: Selection of HED from the most appropriate species*

The HED derived from the rat, 300 mg/day, is the more conservative HED.

#### *Step 4: Selection of safety factor*

Based on applying a safety factor of 10 to the HED of 2880 mg/day, 288 mg/day is considered a safe dose based on toxicity data. However, this 288 mg/day dose exceeds the proposed MRSD, see step 5.

#### *Step 5: Consideration of the Pharmacologically Active Dose (PAD)*

The estimated human therapeutic dose is 35 mg once daily. Applying a safety factor of 10 to ensure the first does in healthy volunteers is reasonably below the anticipated therapeutic dose, the recommended safe starting dose is 4 mg.

### 1.3.2 Maximum dose and dose escalation

Based on the cross-species comparison of vanin-expression ([Section 1.2.1](#)), the dog was chosen as the most relevant toxicological species to humans. Although the NOAEL in dog was determined to be 100 mg/kg/day, the NOEL of 30 mg/kg/day (corresponded to a  $C_{\max}$  of 32,900 nM and  $AUC_{0-24}$  of 157,000 nM•h - male) was chosen to determine safety exposure

Proprietary confidential information © 2019 Boehringer Ingelheim International GmbH or one or more of its affiliated companies

margins due to a not-reversible increase in mean ALT and a reversible decrease in thymus size at the NOAEL-level.

The maximum allowable systemic exposure of BI 764122 will be 32,900 nM for  $C_{max}$  and 157,000 nM·h for  $AUC_{0-24}$  in this study. It is based on findings in the 4-week dog toxicological study and represents a safety factor of 42 for  $C_{max}$  and 31 for  $AUC$  as compared to the exposure at NOEL (see [Table 1.2.3: 2](#)).

To prevent exposure beyond the above predetermined safety margins in this trial, preliminary PK data of preceding DGs will be provided to estimate the expected mean exposure of the next DG (see [Section 7.3.2](#)). The next higher dose level will only be administered, if predicted mean values of  $C_{max}$  and  $AUC_{0-24}$  do not exceed the predefined maximum exposure threshold.

In the SRD part of this trial, the following dose levels of BI 764122 are intended to be investigated: 4 mg, 12 mg, 25 mg, 50 mg, 100 mg, 200 mg, 300 mg and 400 mg.

Dose escalation will start with 4 mg (see [Section 1.3.1](#)). Decreasing escalation factors between escalating steps will be applied: 3, up to a dose of 12 mg; thereafter about 2, up to a dose of 200 mg, 1.5 up to a dose of 300 mg, and about 1.33 up to a dose of 400 mg. Should at this dose the therapeutic window not be sufficiently characterized, a substantial amendment will describe further escalation steps.

In the FE part, the dose of 50 mg BI 764122 is intended to be investigated corresponding to an assumed (high) therapeutic dose.

## **1.4 BENEFIT - RISK ASSESSMENT**

Participation in this clinical trial is without any (therapeutic) benefit for healthy subjects. Their participation, however, is of major importance for the development of BI 764122, which represents a novel approach for the treatment of patients with Crohn's disease.

Subjects are exposed to risks of study procedures and risks related to the exposure to the trial medication.

### **1.4.1 Expected benefit for the target indication**

BI 764122, a first-in-class vanin inhibitor, will be developed in CD. There is a substantial unmet medical need for agents with greater efficacy than current therapies, like aminosalicylates (e.g. 5-ASA), glucocorticoids, immunomodulator agents (azathioprine or 6-MP), biologic TNF $\alpha$  inhibitors (TNFi), or other biologic options (vedolizumab, ustekinumab). Concerns over infection- and lymphoma risks attached to some of these treatments remain. Treatment options for fistulizing and fibrotic disease are limited.

In CD, direct barrier injury is believed to be (at least partially) channeled through vanin enzymes and their product, cysteamine. By reducing cysteamine levels, a vanin inhibitor is expected to lead to direct epithelial barrier repair, resulting in mucosal healing, and to attenuate the chronic inflammation that is underlying the disease. Oral medicines with a novel mode of action that includes repair of epithelial barrier would address the unmet medical need in CD.

#### 1.4.2 Procedure-related risks

The use of an indwelling venous catheter or venepuncture for e.g. blood sampling may result in mild bruising and, in rare cases, in transient inflammation of the wall of the vein, or nerve injury, potentially resulting in paraesthesia, reduced sensibility, and/or pain for an indefinite period.

The total volume of blood withdrawn per subject during the entire study will not exceed the volume of a normal blood donation (500 mL). No health-related risk to healthy subjects is expected from withdrawal of this volume of blood.

#### 1.4.3 Drug-related risks and safety measures

Factors of risk may derive from particular knowledge or the lack thereof, regarding the mode of action, the nature of the target, the relevance of animal models and/or findings in non-clinical safety studies.

##### 1.4.3.1 Mode of action and nature of the target

Vanin-1 and -2 are extracellular enzymes expressed in humans on epithelial (lung, kidney, and intestinal tract), liver-, and immunological cells. It is shed in significant amounts into the extracellular milieu, and is found in most tissues. Its function is to convert pantetheine into pantothenic acid and cysteamine. Through the production of cysteamine, vanin is directly impacting extracellular metabolic homeostasis of different tissues by chemically reducing and depleting cysteine, resulting in increased oxidative stress, endoplasmic reticular stress, and disruption and eventual destruction of tissue. Therefore, it is expected that vanin inhibition will directly restore tissue metabolite homeostasis and redox balance leading to tissue repair in CD-patients.

As described in [Section 1.2.1](#), the human missense SNP (rs2272996) in the gene, encoding vanin-1, is associated with decreased blood pressure [[R18-2692](#)]. Considering this data as well as the findings from the dog telemetry GLP study, blood pressure and heart rate will be closely monitored after BI 764122 administration.

In GLP toxicology studies with BI 764122, there were no adverse histological pancreas findings or a lack of glycemic control. However, considering the conflicting literature, described in [Section 1.2.1](#) about pancreatic islet cell survival, fasting blood glucose levels will be closely monitored as a precautionary measure.

Since there might be a relationship between vanin inhibition and acetaminophen (paracetamol) induced liver toxicity, in this study, acetaminophen will be strictly prohibited as concomitant medication.

##### 1.4.3.2 Relevance of animal models

Vanin-1 expression is well-conserved and aligned between human and rodent species. However, as rodents lack vanin-2, there is a considerable discrepancy between species. In dogs, vanin-1 mRNA levels are high in the lung, liver, spleen and kidney. Comparative expression in tissues is generally lower in the rat, although tissue distribution is comparable.

Proprietary confidential information © 2019 Boehringer Ingelheim International GmbH or one or more of its affiliated companies

While dogs possess a vanin-2 gene, its expression in dog tissues is not characterized. In cynomolgus monkey, tissue distribution of both Vanin-1 and -2 isoforms are broadly comparable to human.

#### 1.4.3.3 Findings in non-clinical safety studies

BI 764122 has a low risk for QT prolongation. The observed decrease in blood pressure with compensatory increases in heart rate in the GLP dog telemetry study at 300 mg/kg may be related to the pharmacological inhibition of Vanin. Autonomic, behavioral, sensorimotor and neuromuscular changes at 6 hours post dose were seen after the administration of 1000 mg/kg to rats. These effects were transient and had reverted by 24 hours post dose.

Toxicological data of BI 764122 support clinical studies in men with daily oral administration for up to 28 days. Results from 4-week GLP studies suggest a NOAEL of 100 mg/kg/day in dog (corresponded to  $C_{max}$  of 159,000 nM and  $AUC_{0-24}$  of 1,070,000 nM•h - male and female combined) and a NOEL of 30 mg/kg/day (corresponded to  $C_{max}$  of 32,900 nM and  $AUC_{0-24}$  of 157,000 nM•h - male). The risk of genotoxicity and phototoxicity is low. Carcinogenicity and local tolerance has not yet been examined. Signs of reproductive toxicity were seen in male rats at 1000 mg/kg/day (abnormal spermatogenesis).

#### 1.4.3.4 Drug induced liver injury

Although rare, a potential for drug-induced liver injury (DILI) is under constant surveillance by sponsors and regulators. Therefore, this trial requires timely detection, evaluation, and follow-up of laboratory alterations in selected liver laboratory parameters to ensure subjects' safety; see also [Section 5.2.6.1.4](#), adverse events of special interest.

#### 1.4.3.5 Risk minimization (safety precautions and stopping rules)

The following risk minimization measures, including safety precautions and stopping rules, will be implemented in this study:

- Careful selection of starting dose, as described in [Section 1.3.1](#).
- Decreasing escalation factors with increasing doses, as described in [Section 1.3.2](#). Dose escalations will only be allowed after documented interim safety reviews (see [Section 3.1.1](#)).
- Preliminary measurement of BI 764122 pharmacokinetics ( $C_{max}$ ,  $AUC_{0-24}$ ; see [Section 7.3.2](#)). The expected exposure in the next higher DG will be estimated based on preliminary PK data of preceding DGs. The next higher dose level will only be administered, if estimated mean values of  $C_{max}$  and  $AUC_{0-24}$  do not exceed the maximum acceptable human exposure (see [Section 1.3.2](#)).
- For safety reasons, division of each DG of 8 subjects (6 on active treatment, 2 on placebo) into 3 staggered cohorts. On the first study day of each dose level, 2 subjects (Cohort 1) will be treated (one with active treatment, the other with placebo). On the second study day, the next 2 subjects (Cohort 2) will be treated (two with active

Proprietary confidential information © 2019 Boehringer Ingelheim International GmbH or one or more of its affiliated companies

treatment). On the third study day of each dose level, the remaining 4 subjects (Cohort 3) will be treated (three with active treatment, one with placebo). If BI 764122 was safe and well tolerated in Cohort 1, the study will continue with Cohort 2. If it was safe and well tolerated in the preceding cohorts, the study will continue with Cohort 3. Between the first application of BI 764122 in each cohort, there will be a time interval of at least 24 h which is expected to cover the peak exposure of the compound. In Cohort 2 and 3, subjects will be dosed at least 1 hour apart.

- A monitoring of safety laboratory with specific focus on glycemic control, hepatic- and hematological integrity (see [Flow Chart](#)).
- An ECG monitoring including continuous ECG measurement over 4 hours post dose to cover the anticipated period of highest drug exposure and additional repeated single or triplicate 12-lead ECGs over 72 hours following drug administration. Dose escalation would be stopped as soon as at least 2 subjects at one dose level showed relevant QT prolongation (see [Section 3.3.4.3](#)).
- Safety monitoring (including e.g. vital signs and adverse events) with a special focus on blood pressure and heart rate measurements.
- Hospitalization of subjects at the trial site for at least 24 hours after study drug administration at each dose level. Based on an anticipated half-life for BI 764122 of about 3.3 h, this is expected to cover the period of highest risk/ peak effect. During in house-confinement, subjects will be under medical observation and thoroughly monitored for both expected and unexpected adverse events.
- Application of the next higher dose, only if the respective dose of BI 764122 is safe, shows acceptable tolerability, and no stopping criterion is met (see [Section 3.3.4.3](#)). At least 7 days will be maintained between the first drug administration to subjects in the previous DG and the first drug administration to subjects in the subsequent DG.
- Exclusion of acetaminophen as concomitant medication.
- As reproductive toxicity studies have not yet been conducted, women will not be enrolled in this study.

#### **1.4.4      Overall assessment**

BI 764122, a first-in-class vanin inhibitor, has not yet been applied to humans. Despite the novelty of the target, non-clinical safety data in relevant animal species, the inhibitory mode of action as well as the risk assessment suggest that BI 764122 is not a high-risk compound and support the application of single doses of BI 764122 in this first-in-man trial. Based on the risk mitigation strategy, comprising of safety precautions and stopping rules, healthy subjects should not be exposed to undue risks by the intake of BI 764122. Healthy volunteers are not expected to have any direct benefit from participation in this trial, as is usually the case in phase 1 studies. Considering the high medical need for a novel, effective and safe

Proprietary confidential information © 2019 Boehringer Ingelheim International GmbH or one or more of its affiliated companies

treatment for Crohn's disease, it is believed that the benefit of this trial outweighs the potential risks and justifies exposure of healthy volunteers to BI 764122.

## **2. TRIAL OBJECTIVES AND ENDPOINTS**

### **2.1 MAIN OBJECTIVES, PRIMARY AND SECONDARY ENDPOINTS**

#### **2.1.1 Main objectives**

The main objectives of this trial are to investigate safety, tolerability and pharmacokinetics (PK) of BI 764122 in healthy male subjects following oral administration of single rising doses.

The objective of the food effect (FE) part is to investigate the relative bioavailability of BI 764122 under fed and fasted conditions.

#### **2.1.2 Primary endpoint**

The primary endpoint for assessment of safety and tolerability of BI 764122 is the percentage of subjects with drug-related adverse events.

#### **2.1.3 Secondary endpoint**

The following pharmacokinetic parameters will be determined for BI 764122 if feasible:

- $AUC_{0-\infty}$  (area under the concentration-time curve of the analyte in plasma over the time interval from 0 extrapolated to infinity)
- $C_{\max}$  (maximum measured concentration of the analyte in plasma)

Proprietary confidential information © 2019 Boehringer Ingelheim International GmbH or one or more of its affiliated companies

### 3. DESCRIPTION OF DESIGN AND TRIAL POPULATION

#### 3.1 OVERALL TRIAL DESIGN AND PLAN

This first-in-man (FIM) study consists of a single rising dose (SRD) and a food effect (FE) part. A total of 76 healthy male subjects is planned to participate in the trial, thereof 64 in the SRD part and 12 in the FE part. Additional subjects may be entered in the SRD part (see below). Thus, the actual total number of subjects may exceed 76 but not 92 subjects entered.

##### 3.1.1 Single rising dose (SRD) part

The SRD part is designed as single-blind, partially randomised and placebo-controlled within parallel (sequential) DGs.

It is planned to include a total of 64 healthy male subjects in the SRD part. The subjects will be assigned to 8 groups consisting of 8 subjects per group; the groups will be dosed sequentially (see [Table 3.1: 1](#)). The investigator (after consultation with the sponsor) is allowed to alter the scheduled DGs (e.g., add low and/or intermediate DGs) on the basis of experience gained during the study (for instance, based on safety and/or preliminary PK data), provided the planned and approved highest dose is not exceeded. Thus, the actual number of subjects entered in the SRD part may be more than 64 but is not to exceed 80. Such changes, which are based on preliminary PK data, may be implemented via non-substantial CTP amendments. Changes, based on safety findings, will be implemented only via substantial CTP amendments.

Within each DG, 6 subjects will receive BI 764122 and 2 will receive placebo. Only one dose is tested within each DG. For safety reasons, each DG will consist of 3 cohorts. The trial medication will be administered in the following order:

- Cohort 1 (fixed order): the 1st subject on active treatment and the 2nd subject on placebo (in total 2 subjects)
- Cohort 2 (fixed order): 2 subjects on active treatment (in total 2 subjects)
- Cohort 3 (randomised): 3 subjects on active treatment and 1 subject on placebo (in total 4 subjects)

Between first drug administrations in Cohort 1 and 2, there will be a time interval of at least 24 hours which is expected to cover the peak exposure of BI 764122. If BI 764122 was safe and well tolerated in Cohort 1, the study will continue with Cohort 2. The 2 subjects of Cohort 2 will be dosed at least 1 hour apart. If BI 764122 was still safe and well tolerated in all subjects of Cohort 1 and 2, the study will proceed at least 24 hours after the first drug administration in Cohort 2 with the 4 subjects of Cohort 3, who will be dosed at least 15 minutes apart.

The DGs to be evaluated are outlined in [Table 3.1: 1](#) below.

Table 3.1: 1

Dose groups (DGs)

DG	1	2	3	4	5	6	7	8
Dose (mg)	4	12	25	50	100	200	300	400
Number of subjects	8	8	8	8	8	8	8	8
Subjects receiving placebo	2	2	2	2	2	2	2	2
Subjects receiving BI 764122	6	6	6	6	6	6	6	6

The groups will be dosed consecutively in ascending order, and a time interval of at least 7 days will be maintained between the last drug administration to subjects in the previous DG and the first drug administration to subjects in the subsequent DG. The decision to escalate to the next DG will be based upon safety, tolerability and pharmacokinetic data of all subjects of the preceding DGs. The next DG will only be treated, if, in the opinion of the investigator, no safety concerns have arisen in the preceding DGs (i.e. no dose-limiting events occurred), and if none of the pre-specified trial-specific stopping criteria have been met (see [Section 3.3.4.1](#)).

A documented Safety Review must take place prior to each dose escalation. Furthermore, an unscheduled safety review meeting can be requested at any time by the Principal Investigator (or an authorised deputy) or the sponsor of the study (for instance, due to the occurrence of any unforeseen adverse events).

Although no formal Safety Review meeting will take place within a given DG, safety will be continuously monitored during this trial. An individual will only be dosed in the absence of any safety concern (i.e. no dose-limiting events occurred) and, if none of the pre-specified trial-specific stopping criteria have been met (see [Section 3.3.4.1](#)).

At minimum, data from 4 subjects on active drug need to be available for escalation to a higher dose. For the minimum dataset with regards to preliminary PK data, see [Section 7.4](#). The minimum data set for review consists of the following:

- AEs in the current and preceding DGs up to at least 48 h post dosing, including clinically relevant findings from ancillary safety testing listed below (Note: AEs may be ongoing at the time of Safety Review and AE information may be subject to change prior to Database Lock)
- Results from 12-lead ECG and continuous ECG monitoring in the current and preceding DGs up to at least 48 h post dosing
- Vital signs in the current and preceding DGs up to at least 48 h post dosing
- Clinical laboratory tests in the current and preceding DGs up to at least 48 h post dosing
- Preliminary PK data for the selected time as per [Section 7.4](#). For escalation from DG 1 to DG 2, preliminary PK data are not required
- Check of criteria for stopping subject treatment, as per [Section 3.3.4.1](#)

The decision to escalate the dose will be made jointly by the Principal Investigator (or an authorised deputy) and the Clinical Trial Lead (or an authorised deputy) after in-depth analysis of all available safety data, especially SAEs (if occurred), AEs, and out-of-range

Proprietary confidential information © 2019 Boehringer Ingelheim International GmbH or one or more of its affiliated companies

laboratory results (if considered clinically relevant). In addition and depending on the results and findings, suitable experts from the sponsor or external institutions may be consulted on an 'as needed' basis. In these cases, expert recommendations will be documented in the minutes of the Safety Review and considered for the decision making. Dose escalation will only be permitted, if no safety concerns exist neither in the opinion of the Principal Investigator (or an authorised deputy) nor the Clinical Trial Lead (or an authorised deputy).

Safety Reviews can be conducted face-to-face or by video/telephone conference. The Clinical Trial Lead is responsible for the organisation and minutes of the reviews. Minutes will be signed off by the Principal Investigator (or an authorised deputy) and Clinical Trial Lead (or an authorised deputy), and will be filed in the ISF and TMF.

An overview of all relevant trial activities is provided in the [Flow Chart](#). For visit schedules and details of trial procedures at selected visits, see [Sections 6.1](#) and [6.2](#), respectively.

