#### 3.3.4.1 Discontinuation of trial treatment

An individual subject will discontinue trial treatment, if:

1. The subject wants to discontinue trial treatment, without the need to justify the decision
2. The subject has repeatedly shown to be non-compliant with important trial procedures and, in the opinion of both, the investigator and sponsor representative, is not willing or able to adhere to the trial requirements in the future
3. The subject needs to take concomitant medication that interferes with the investigational medicinal product or other trial treatment
4. The subject can no longer receive trial treatment for medical reasons (such as surgery, adverse events [AEs], or diseases)
5. An AE or clinically relevant laboratory change or abnormality occurs that the investigator assesses as warranting discontinuation of treatment. This may include cases of sustained symptomatic hypotension (BP <90/50 mmHg) or hypertension (BP >180/100 mmHg), clinically relevant changes in ECG requiring intervention, or unexplained hepatic enzyme elevations at any time during the trial
6. The subject has an elevation of AST and/or ALT  $\geq 3$ -fold ULN and an elevation of total bilirubin  $\geq 2$ -fold ULN (measured in the same blood sample) and/or needs to be followed up according to the DILI checklist provided in the ISF

In addition to these criteria, the investigator may discontinue subjects at any time based on his or her clinical judgment.

Even if the trial treatment is discontinued, the subject remains in the trial and, given his agreement, will undergo the procedures for early treatment discontinuation and follow up as outlined in the [Flow Chart](#) and [Section 6.2.3](#).

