### **3.3.4.3 Discontinuation of the trial by the sponsor**

Boehringer Ingelheim reserves the right to discontinue the trial overall or at a particular trial site at any time for any of the following reasons:

1. Failure to meet expected enrolment goals overall or at a particular trial site.
2. New toxicological findings, serious adverse events, or any safety information invalidating the earlier positive benefit-risk assessment. Dose escalation will be terminated, if more than 50% of subjects at one dose level show drug-related and clinically relevant adverse events of moderate or severe intensity, or if at least one drug-related serious adverse event is reported
3. Violation of GCP, or the CTP, or the contract with BI impairing the appropriate conduct of the trial
4. The sponsor decides to discontinue the further development of the investigational product
5. Dose escalation will be stopped, if at least 2 subjects on active treatment at one dose level have relevant individual QT prolongations, i.e. a QTc increase of greater than 60 ms from baseline in connection with absolute QT or QTc greater than 500 ms, as confirmed by a repeat ECG recording
6. Dose escalation will be stopped, if the  $C_{max}$  or  $AUC_{0-24}$  of at least 1 subject of one DG increases above the following exposure thresholds or if the estimated gMean exposure is expected to exceed a  $C_{max}$  of 32,900 nM or an  $AUC_{0-24}$  of 157,000 nM\*h. Estimation will be done based on preliminary PK results of preceding DGs (see [Section 7.4](#))
7. Occurrence of severe non-serious adverse events considered as drug-related by the investigator in 2 subjects of the same dose

The investigator/ trial site will be reimbursed for reasonable expenses incurred in case of trial termination (except, if item 3 applies).

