## **7.4 INTERIM ANALYSES**

No interim analysis is planned.

In the SRD part, a preliminary analysis of PK parameters ( $AUC_{0-24}$  and  $C_{max}$  of BI 764122) provided as individual values and geometric means of all available data from at least 4 subjects on active treatment per current dose level, supported by all the available data from subjects of preceding dose levels, will be performed before proceeding to the next higher dose level. For escalation from DG 1 to DG 2, and after the last DG, preliminary PK data are not required, see [Section 3](#).

The pharmacokinetic parameters  $AUC_{0-24}$  and  $C_{max}$  of BI 764122 will be calculated according to the BI SOP 'Standards and processes for analyses performed within Clinical Pharmacokinetics/Pharmacodynamics' ([001-MCS-36-472](#)). The non-compartmental analysis will be performed using a validated software program such as Phoenix WinNonlinTM software (version 6.3 or higher, Certara USA Inc., Princeton, NJ, USA). A quality check of the preliminary data will be performed.

In contrast to the final PK calculations, the preliminary analysis will be based on planned sampling times rather than on actual times, regardless of whether actual times were within the time windows. Therefore, minor deviations may occur between preliminary and final results. The preliminary analysis will provide individual and mean concentration/effect-time profiles and summary statistics of individual values without subject identification information. The preliminary results will be distributed to the investigator and the trial team.

Depending on the results of available preliminary PK analyses and the tolerability and safety of the compound, changes to the dosing schedule (e.g., additional intermediate doses), and additional PK preliminary analysis may be performed if requested by the Clinical Trial Lead, the investigator, or Trial Clinical Pharmacokineticist. Preliminary PK results will not be reported in the CTR. No formal preliminary PK report will be written.

No inferential statistical interim analysis is planned. However, after completion of each DG the investigator (or his or her deputy) is allowed to postpone further dose progression until a preliminary analysis of the data has been performed.

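### Escalation must stop if any one subject exceeds the exposure cap, but the Safety Review may proceed on 4 of 6 active subjects while assays are pending, and two sentences of Protocol 3.1.1 omit the section that holds the stops

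*Protocol*

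**What the plan says.** Protocol 3.3.4.3 item 6 has two limbs. Escalation stops if Cmax or AUC0-24 "of at least 1 subject of one DG increases above the following exposure thresholds", or if the projected gMean of the next dose is expected to exceed 32,900 nM or 157,000 nM·h. I read both limbs as using the same two thresholds.

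On the data needed, 3.1.1 states: "At minimum, data from 4 subjects on active drug need to be available for escalation to a higher dose". Section 7.4 asks for "individual values and geometric means of all available data from at least 4 subjects on active treatment per current dose level". Table 3.1: 1 gives six active subjects per DG. Section 3.1.1 also bases the decision on "pharmacokinetic data of all subjects of the preceding DGs", so four is a minimum and not the target. No preliminary PK is required for DG 1 to DG 2.

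On the stops, 3.1.1 makes the next DG conditional on no dose-limiting events "and if none of the pre-specified trial-specific stopping criteria have been met", and cites 3.3.4.1. The sentence on dosing within a DG, which begins "An individual will only be dosed in the absence of any safety concern (i.e. no dose-limiting events occurred", cites 3.3.4.1 for the same criteria. That section opens with "An individual subject will discontinue trial treatment, if" and lists reasons to discontinue one subject. The escalation stops (adverse event proportion or drug-related SAE, QT, exposure, severe adverse events) are 3.3.4.3 items 2, 5, 6 and 7. Section 1.4.3.5 cites 3.3.4.3 correctly. The last bullet of the minimum data set, "Check of criteria for stopping subject treatment, as per" 3.3.4.1, points to the right place for subject-level criteria, but no bullet covers the escalation stops.

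**The concern.** A gMean can be estimated from four of six values. A rule that stops on any one subject is different: each unread subject is one in whom a breach cannot be seen. Because the floor is not tied to a reason, a team can meet the stated minimum with one or two assays outstanding and escalate past a breach that is already in the freezer. From 100 mg upward, the next DG then starts at 1.33 to 2 times the dose, with up to six active subjects staggered as 1, 2 and 3.

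A late result could still halt dosing part-way through that DG. However, the sentence in 3.1.1 that would do this is one of the two that point only to the subject-level section. A team that works from the minimum data set is not prompted to check the escalation stops.

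**Working it through.** **Reference figures.** The plan gives no operating characteristic for its stopping rules. Its only related figures are the multiples of the predicted therapeutic exposure, and they reproduce: 32,900/788 = 41.8 (stated 42) and 157,000/5,137 = 30.6 (stated 31).

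**Step 1: miss chance given a breach.** Suppose k of six active subjects are above the cap and m are read, and the unread ones are a random subset. Then P(none seen) = C(6−k, m)/C(6, m).

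- k = 1: m = 4 gives 5/15 = 33%; m = 5 gives 1/6 = 17%; m = 6 gives 0.
- k = 2: m = 4 gives 1/15 = 7%; m = 5 gives 0.

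**Step 2: if exposure follows prediction.** Scale the predicted AUC0-24 of 5,137 nM·h at 35 mg (1.2.4) linearly. This is conservative, because 1.2.4 expects a less than proportional increase.

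- 100 mg: 5,137 × 100/35 = 14,677, or 9% of 157,000.
- 200 mg: 29,354, or 19%.
- 300 mg: 44,031, or 28%.

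AUC is the tighter limb: Cmax at 300 mg scales to 788 × 300/35 = 6,754, or 21% of 32,900.

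Assume lognormal exposure with σ = √ln(1 + gCV²), so p = 1 − Φ(ln(cap/gMean)/σ) is the chance that one subject is above the cap. P(breach exists, none read) is (1−p)^4 − (1−p)^6 with four read and (1−p)^5 − (1−p)^6 with five. The documents give no gCV for exposure between subjects; 30% and 50% are assumed. At 300 mg with gCV 50%, p = 0.0036, so the result is 0.7% with four read and 0.35% with five. At 200 mg with gCV 50% it is 0.04% with four read.

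**Step 3: stress case.** Put the true gMean at the most that the projection limb allows before steps of 2, 1.5 and 1.33: 50%, 67% and 75% of the cap. At 100, 200 and 300 mg this needs 78,500/14,677 = 5.3, 104,667/29,354 = 3.6 and 117,750/44,031 = 2.7 times the predicted AUC. Escalating past a breach also requires that the gMean of those read, projected in proportion to dose, stays within the cap. I added that condition by simulation (2 million draws per row).

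| gCV | gMean/cap | p | Unread breach, 4 read | and projection passes, 4 read | and projection passes, 5 read |
|---|---|---|---|---|---|
| 30% | 0.50 | 0.009 | 1.7% | 0.9% | 0.5% |
| 30% | 0.67 | 0.084 | 11.3% | 7.2% | 3.6% |
| 30% | 0.75 | 0.164 | 14.7% | 11.2% | 5.3% |
| 50% | 0.50 | 0.071 | 10.2% | 6.3% | 3.1% |
| 50% | 0.67 | 0.195 | 14.8% | 11.9% | 5.5% |
| 50% | 0.75 | 0.271 | 13.2% | 12.0% | 5.2% |

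**Step 4: time for the assay.** Section 3.1.1 requires at least 7 days from the last dose of one DG to the first dose of the next. After the last 24 h sample that leaves at least 7 − 1 = 6 days.

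**Step 5: margin above the cap.** The cap is the dog NOEL. The dog NOAEL is 159,000/32,900 = 4.8 times higher for Cmax and 1,070,000/157,000 = 6.8 times higher for AUC.

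**The case against.** The strongest reply is that four is a floor and not the plan. Section 3.1.1 speaks of all subjects and 7.4 of all available data shown as individual values, so any assayed breach is visible, and nothing permits a result to be ignored. SRD subjects are not replaced (3.3.5 covers the FE part only), so some floor is needed. All of this stands. It does not close the gap, because available is undefined and the floor is not confined to data that cannot be obtained.

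Four stronger readings are tempting, and the documents do not support them.

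- **A shorter assay window.** Section 1.4.3.5 counts 7 days from the first dose of the previous DG, from which a reader might infer only 4 days after Cohort 3's 24 h sample. Both intervals are minimums, and meeting 3.1.1 always meets 1.4.3.5, so the compliant window is at least 6 days.
- **The escalation stops do not bind.** They do. Section 1.4.3.5 makes the next dose conditional on them and cites 3.3.4.3. The Principal Investigator and the Clinical Trial Lead must also both be free of safety concerns. The pointers are errors of reference.
- **33% is the risk of escalating past a breach.** It is conditional on exactly one breach and exactly four subjects read. The documents give no probability for either.
- **The same gap affects the QT and severe-event stops.** Clinical data to 48 h should normally exist for all dosed subjects well before the next DG can start. The realistic gap is PK still in assay.

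It is also fair that the minimum data set already lists the adverse events, ECGs and PK from which the stops would be judged. A line that names the stops is a prompt, not new data.

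**Conclusion.** The point holds as a minor one. A stop on any one subject is paired with a data floor of four of six that a pending assay can satisfy. Two sentences of 3.1.1 omit the section where the escalation stops are, and the minimum data set has no line for them.

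The practical risk is small. When four are read, the chance of an unseen breach is below 1% if exposure follows prediction, and about 1% to 12% in the stress case once the gMean limb is applied (0.5% to 5.5% when five are read). These figures assume that the unread subjects are a random subset, lognormal exposure, gCV of 30% to 50%, and projection in proportion to dose. They are conditional on the number read, so no overall risk can be stated. The 6-day window makes outstanding assays avoidable, and the cap sits well below the dog NOAEL. The case for acting is that the rule exists for the situation in which prediction fails, no human data exist yet, and the repair is cheap.

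**What to change.** (a) In 3.1.1 and 7.4, state that the one-subject condition of 3.3.4.3 item 6 is assessed on all preliminary Cmax and AUC0-24 values obtainable from every active subject dosed in the current DG. A subject may be missing for a parameter only if it cannot be determined (for example early withdrawal, or lost or non-evaluable samples), and not because an assay is pending. Record the reason in the Safety Review minutes, and never use fewer than four subjects. Wording this by parameter means that a subject with a Cmax but no AUC0-24 does not block escalation. Keep the DG 1 to DG 2 exception.

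(b) In the two 3.1.1 sentences on trial-specific stopping criteria, add Section 3.3.4.3 items 2, 5, 6 and 7 alongside 3.3.4.1. Adding is better than replacing: as written, the individual-dosing sentence also brings in the subject-level criteria, including the liver criterion, and those should stay.

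(c) Add a bullet to the minimum data set to check the escalation stops of 3.3.4.3, and keep the 3.3.4.1 bullet.

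Cost: protocol wording, and earlier assay of up to about 30 samples per DG (15 samples from pre-dose to 24 h for each of two subjects), which are assayed for the final PK anyway. The downside is a possible short delay of the next DG if an assay is late.
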